9.1.1 Operating characteristics of the 3+3 design

Since true probabilities of DLTs under specific dose levels are unknown, four theoretical scenarios are presented to illustrate operating characteristics of the 3+3 design in different locations of the MTD. The calculation was performed considering all possible trial pathways for the standard 3+3 design (Wheeler et al., 2016).

Two extreme scenarios are considered, where the true MTD is lower or higher than dose levels tested in the study. Then, two scenarios where the MTD is within the interval of dose levels that are tested in the study.

Operating characteristics of 3+3 design with 3 dose levels under 4 different scenarios are in Table 14.

Table 14: Operating characteristics of 3+3 design with 3 dose levels under 4 different scenarios.

Clinical Study: ES2B-C001-S01 EU CT No.: 2024-516333-12-00

9.2 Analysis Sets

Safety Set: will include all patients who received at least 1 dose of the trial drug. All safety/tolerability and DLT analyses will be performed using this analysis set and will be descriptive, with no statistical inference to be drawn from the data.

Immunogenicity Set: will include all patients who received at least 1 dose of the trial drug and have provided immunogenicity data. All immunogenicity analyses will be performed using this population.

Efficacy-evaluable Set: will include all patients receiving at least 1 dose of the trial drug and who have provided at least 1 tumor evaluation at baseline and 1 tumor evaluation following treatment administration.

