Expansions of the cohorts are foreseen without further amendment. Expansion of cohorts will be considered in the case of high variability of the emerging immunogenicity data or in case it appears desirable to obtain more safety data from a given cohort.

Patients will be considered to have completed the study protocol if they attend an end of study (EOS visit) 6 weeks after the last dose of the primary vaccination series.

Booster doses may be offered to patients under a compassionate use program (CUP) based on the investigator's choice for patients with at least stable disease or better who show a good immunologic response and a good tolerability, if they wish to receive such boosters.

Test Product ES2B-C001:

Type: Vaccine

Formulation: solution for intramuscular injection

Strength: 3.0 mg/mL

Route of administration: intramuscular (I.M.)

Medicinal Product (IMP)

Investigational

Type: Adjuvant

[figure not shown]
Formulation: 3.0 mL solution; mixed in 1:1 (v/v) ratio with ES2B-C001

	Strength: N/A
	Route of administration: intramuscular (I.M.)
Number of Participants	9 patients (3 per cohort) will be enrolled in the dose escalation parts with 3 dose levels each. Up to 3 expansions of cohorts are planned, which may increase cohort sizes to 6-9 patients. In total, up to 27 patients may be dosed (not accounting for replacement of potential dropouts).
Inclusion Criteria	Subjects who meet the following criteria will be eligible to participate in the clinical study:
Exclusion Criteria	Subjects who meet one or more of the following criteria will not be considered eligible to participate in the clinical study:

Clinical Study: ES2B-C001-S01 EU CT No.: 2024-516333-12-00

expreS2ion BIOTECH

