4.3 Dose escalation

A DSMB will be appointed to oversee the trial. The composition and responsibilities of the DSMB is described in a dedicated charter, which will include additional instructions for the dose escalation procedure.

The decision to escalate the dose to the next dosing cohort or initiate the expansion part will be taken by the sponsor based on the DSMB recommendations. For the decision of dose escalation, AEs collected during the DLT period will be assessed by the DSMB. Other available data beyond the DLT evaluation period for all patients in the trial will also be assessed before a decision on escalation to the next dose level can be taken. Dose escalation rules will be based on the number of patients with AEs, specifically DLTs (Section 4.3.2). The DSMB will base recommendations on an evaluation of accumulated safety data and may include other available data, including data on immunogenicity (antibody titers) in their review.

Patients who discontinue for reasons other than toxicity before having DLT evaluable safety data may be replaced at sponsor's discretion.

A schedule of trial procedures is provided in Section 1.3. The administration of adjuvanted and non-adjuvanted ES2B-C001 is described in Section 6 and the trial assessments are described in Section 8.

The dose escalation will include 3 planned dose level cohorts with adjuvanted ES2B-C001 (Section 6.2).

Enrollment will be fully staggered in each of the populations, meaning that an observation period of 3 weeks plus 24 hours is foreseen before the second patient is dosed in one cohort. Dosing of the next subject in each cohort should not take place until 1 week after the preceding patient has received the first dose. Prior to dosing the second patient, safety and reactogenicity data from the previous patient will be discussed at a pre-dosing call between PI(s), CRO medical monitor, and

Clinical Study: ES2B-C001-S01 EU CT No.: 2024-516333-12-00

Sponsor. At subsequent administrations, pre-dosing calls will be scheduled if safety concerns warrant it. This will ensure an evaluation of safety prior to administration of the next patients.

Any safety concerns, such as potential DLTs and/or events that may meet a criterion for initiation of rescue medication, will be escalated to the DSMB who will review accumulated safety data and may provide recommendations for trial adjustments e.g., applying additional overnight stays for patients.

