7.1 Discontinuation of Trial Treatment

Patients may stop treatment at any time during the trial at their discretion. The treating physician may, for safety reasons or the well-being of the patient, refrain from dosing at the discretion of the treating physician.

If adjuvanted or non-adjuvanted ES2B-C001 is permanently discontinued, the patient should, if at all possible, have an early termination visit and remain in the trial for follow-up visit 7 and 8. See the SoA (Section 1.3) for data to be collected at the End of Trial and during follow-up.

Discontinuation of trial treatment does not represent withdrawal from the trial.

Patients who discontinue for reasons other than toxicity before having DLT evaluable safety data may be replaced at sponsor's discretion.

A patient should be considered for discontinuation from trial treatment but continue to be monitored in the trial for any of the following reasons:

- Unacceptable toxicity.
- Intercurrent illness of sufficient magnitude to preclude safe continuation of the trial.
- Investigator's judgement on optimal benefit/risk not supporting continuation of the trial for the individual patient.
- Non-compliance with trial requirements (e.g. treatment delay of 28 days or more).
- · Patient's decision.
- Pregnancy during the trial.
- Patient is lost to follow-up.
- Death.

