9.1 Sample Size Determination

This is a phase I study following a traditional 3+3 design, and no formal statistical hypothesis will be tested. The sample size was estimated to be 9 evaluable patients assuming 3 possible dose levels. However, due to the cohort expansion design, a maximum of 27 evaluable patients in total could be dosed.

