9.3.1 Primary endpoint analysis

Total number and incidence of dose limiting toxicities (DLTs), number of patients with DTLs and percentage of patients with DLTs in each dose level and patient population will be reported.

Additionally, the number of DLTs, affected patients and percentage of affected patients will also be reported by preferred term and severity according to CTCAE v5.0 in each dose level and patient population.

The maximum tolerated dose will be determined for each patient population separately as lowest dose level at which ≥33% of patients have record of DLT.

The primary endpoint will be evaluated on the Safety Set.

Clinical Study: ES2B-C001-S01 EU CT No.: 2024-516333-12-00

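### DLT percentages and the ≥33% MTD criterion use everyone dosed, so one replaced, non-evaluable patient can change a reported 2/6 (33.3%) to 2/7 (28.6%), below the criterion

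*Protocol*

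**What the plan says.** Section 9.2 admits to the Safety Set every patient with at least one dose, and continues: "All safety/tolerability and DLT analyses will be performed using this analysis set and will be descriptive". Section 9.3.1 repeats the choice: "The primary endpoint will be evaluated on the Safety Set". It reports the percentage of patients with DLTs per dose level and defines the MTD as the "lowest dose level at which ≥33% of patients have record of DLT". That is the only MTD criterion in the analysis section.

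Elsewhere the protocol thinks in evaluable patients:

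- Section 9.1: "The sample size was estimated to be 9 evaluable patients assuming 3 possible dose levels", with a maximum of 27 evaluable patients.
- Section 4.3: "Patients who discontinue for reasons other than toxicity before having DLT evaluable safety data may be replaced at sponsor's discretion". Section 7.1 repeats this.
- The synopsis gives the 27 without counting replacements, so replacements come on top.

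Sections 4.3.1 and 7.5 act on counts. Two or more patients with a DLT among 6 bar further escalation and halt enrolment. Section 4.3.2 sets the DLT window at 8 weeks from the first administration.

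**The concern.** The protocol accepts that a dosed patient may lack DLT-evaluable data, and it lets the sponsor replace that patient. The analysis section then puts the patient back into the denominator. Someone whose DLT status was never established counts as DLT-free. Whenever at least one DLT has occurred, this pulls the reported percentage down.

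It also lets two of the protocol's own rules part company. The count rule looks at 2 of 6, and the analysis criterion looks at a percentage of everyone dosed. The two thresholds coincide at 2/6, but only just, so one extra patient in the denominator separates them. Determining the MTD is part of the primary objective and the DLT percentage summarises a primary endpoint. The primary result could then fail to show the criterion met at a dose where escalation was stopped for DLTs.

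**Working it through.** **The plan's own figures.** 3 dose levels × 3 patients = 9, and 3 × 9 = 27. Both agree with section 9.1. The content of Table 14 (operating characteristics) is not visible in the text and is not needed here.

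**Inputs from the protocol.** Criterion ≥33% on the Safety Set (9.2, 9.3.1); stop at 2 or more of 6, with cohorts expanded from 3 to 6 after one DLT (4.3.1, 7.5); replacement of non-evaluable patients (4.3, 7.1).

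**Step 1: effect of replaced, DLT-free patients on each possible stop.**

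| Stop among evaluable patients | Extra patients needed to fall below 33% | Result |
|---|---|---|
| 2/6 = 33.3% | 1 | 2/7 = 28.6% |
| 2/3 = 66.7% | 4 | 2/7 = 28.6% |
| 3/6 = 50.0% | 4 | 3/10 = 30.0% |
| 3/3 = 100% | 7 | 3/10 = 30.0% |
| 4/6 = 66.7% | 7 | 4/13 = 30.8% |

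A single extra patient changes the criterion only at 2/6.

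**Step 2: how often a stop is at exactly 2/6.** For a standard 3+3 at one dose with true DLT rate p (assumed values), let P(x/3) be the binomial probability of x DLTs in 3 patients.

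- P(stop) = 1 − [P(0/3) + P(1/3)·P(0/3)]
- P(stop at exactly 2/6) = P(1/3)²

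| p | P(stop) | P(2/6) | Share of stops at 2/6 | Share at 2/3 |
|---|---|---|---|---|
| 0.25 | 0.4001 | 0.1780 | 44% | 35% |
| 0.33 | 0.5656 | 0.1975 | 35% | 39% |
| 0.40 | 0.6907 | 0.1866 | 27% | 42% |

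**Step 3: how often a 2/6 stop carries at least one replaced patient.** The protocol gives no non-evaluable rate. Assume a rate d, independent between patients, with every such patient DLT-free and replaced until 6 are evaluable:

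P(at least one replaced) = 1 − (1 − d)^6 = 0.265, 0.469 and 0.738 for d = 0.05, 0.10 and 0.20.

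**Step 4: share of stopped doses that miss ≥33%.** The 2/6 route is step 2 × step 3. The all-routes figure adds, for each other stop in step 1, its share of stops times the negative-binomial probability of the number of replacements it needs.

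| p | 2/6 route, d = 0.05 / 0.10 / 0.20 | All routes, d = 0.05 / 0.10 / 0.20 |
|---|---|---|
| 0.25 | 0.118 / 0.208 / 0.328 | 0.118 / 0.210 / 0.347 |
| 0.33 | 0.093 / 0.164 / 0.258 | 0.093 / 0.166 / 0.279 |
| 0.40 | 0.072 / 0.127 / 0.199 | 0.072 / 0.129 / 0.222 |

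Almost all of the effect comes from the 2/6 stop.

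**Step 5: opposite extreme.** If each DLT were known at once and enrolment ended at the second one, a patient found non-evaluable after that point would not be replaced. Over d = 5% to 20%, the all-routes shares then fall to about 5–21%, 4–18% and 3–15% for p = 0.25, 0.33 and 0.40.

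**The case against.** The strongest reply has four parts.

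*No decision changes.* Escalation uses counts and DSMB review, the DLT analyses are descriptive, and section 9.3.1 reports numbers of patients beside percentages, so a 2/7 would be visible. This stands, and it limits the point to reporting. It does not remove it, because the criterion in 9.3.1 is a percentage and would be applied to that 2/7.

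*The frequencies are too high.* Section 7.5 halts enrolment at 2 or more DLTs, so some non-evaluable patients would never be replaced. Replacement is discretionary in any case. Moreover, "Discontinuation of trial treatment does not represent withdrawal from the trial", and such patients stay in follow-up where possible, so someone who stops early may still complete the 8 weeks and be evaluable. All of this stands. The step 4 figures are upper-end; with an 8-week window, the effect of the halt alone puts the result between step 4 and step 5. Nothing in the protocol supports any particular non-evaluable rate. The result free of such assumptions is 2/6 against 2/7.

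*The MTD wording is the larger fault.* Section 9.3.1 labels as MTD the lowest dose with at least 33% DLTs, which at 2/6 is the dose where 4.3.1 bars further escalation. This stands as a separate inconsistency. Correcting it alone would leave the denominator as it is.

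*It can be left to the SAP.* This does not stand. Sections 9.2 and 9.3.1 positively assign the Safety Set, and an SAP that used an evaluable set would contradict the protocol.

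**Conclusion.** The concern holds. As written, dosed and replaced patients who gave no evaluable DLT information count as non-DLTs in the DLT percentage and in the MTD criterion. The percentage is biased downwards at any non-zero count. One such patient takes a 2/6 stop from 33.3%, which meets the criterion, to 28.6%, which does not.

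How often this would happen rests on assumed DLT rates of 0.25 to 0.40 and an assumed non-evaluable rate of 5% to 20%. The shares of stopped doses affected are at most 12–35%, 9–28% and 7–22%, and lower once the enrolment halt, discretionary replacement and continued follow-up are allowed for. The live escalation decision is untouched, and section 4.2 still says that an MTD will be established from the accumulated safety data. The change should be made because the primary result can otherwise disagree with the decision it reports, and the correction is cheap.

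**What to change.** In section 9.2, add a DLT-evaluable set: patients with a DLT within the 8-week window, plus patients who completed the window without one and had the exposure the sponsor specifies. In section 9.3.1, use this set for the DLT percentages and the MTD determination. Keep the Safety Set for adverse-event tables and list the DLT-non-evaluable patients there.

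The sponsor must first settle the exposure requirement. The synopsis has the DSMB review once 3 patients have had at least one dose, whereas 4.3.1 requires the last patient to have had the second dose. These sections must be reconciled.

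This change does not repair the MTD wording in 9.3.1. Its threshold is also met by 1/3 = 33.3%, where 4.3.1 adds 3 patients. That wording has to be reconciled with 4.2 and 4.3.1 separately.

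The cost is wording in two sections and one more set to tabulate. Where a non-evaluable patient occurs, the DLT percentage becomes slightly less favourable.

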9.3 Statistical Analyses

In general, continuous data will be summarized using number of available data, mean, standard deviation, median, minimum, and maximum by dose level. Categorical and ordinal data will be summarized using number and percentage of patients by dose level.

The detailed statistical analysis will be described in the SAP.

9.3.1 Primary endpoint analysis

Total number and incidence of dose limiting toxicities (DLTs), number of patients with DTLs and percentage of patients with DLTs in each dose level and patient population will be reported.

Additionally, the number of DLTs, affected patients and percentage of affected patients will also be reported by preferred term and severity according to CTCAE v5.0 in each dose level and patient population.

The maximum tolerated dose will be determined for each patient population separately as lowest dose level at which ≥33% of patients have record of DLT.

The primary endpoint will be evaluated on the Safety Set.

Clinical Study: ES2B-C001-S01 EU CT No.: 2024-516333-12-00

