2.4 Overall Benefit-Risk Conclusion

In conclusion, this trial aims to evaluate the safety profile of the novel HER2-directed vaccine ES2B-C001 with and without adjuvant. The risks for the patients participating in the trial are considered low and it is expected that the polyclonal anti HER2 antibody response will have anticancer effects beneficial to patients participating in the trial. The overall risk-benefit-ratio of participating in this trial is judged to be favorable in patients

3 Trial Objectives and Endpoints

Table 3: Description of the objectives and endpoints of this clinical study.

Objectives	Endpoints			
Primary				
To determine the safety, tolerability, maximum tolerated dose (MTD) for ES2B-C001 alone or in combination with the adjuvant	 Nature and frequency of dose-limiting toxicities (DLTs). Incidence, nature and severity of AEs graded according to the National Cancer Institute (NCI) Common Terminology Criteria for Adverse Events (CTCAE) v5.0. Incidence, nature and severity of injection site reactions according to FDA Guidance on Toxicity Grading Scales in Vaccine Trials (FDA, 2007). 			

Clinical Study: ES2B-C001-S01 EU CT No.: 2024-516333-12-00

Objectives	Endpoints			
Secondary				
To investigate the immunogenicity of ES2B-C001 alone or in combination with the adjuvant	 Immunogenicity as humoral immune response: Total anti-HER2 Immunoglobulin titers in sera by enzyme-linked immunosorbent assay (ELISA). Isotyping of anti-HER2 Immunoglobulins in sera (e.g. IgM, IgG (IgG1-4), IgD, IgE, IgA), Optional and obligatory in the non-adjuvanted and adjuvanted treatment group, respectively. 			
Exploratory				
To determine the preliminary antitumor activity of ES2B-C001 alone or in combination with the adjuvant observed	 Percentage of patients with measurable disease at baseline achieving Complete Remission (CR) or Partial Response (PR) according to RECIST 1.1 as assessed by the investigator during routine follow up. Percentage of patients with Disease Control Rate (DCR) according to RECIST 1.1 as assessed by the investigator during routine follow up. Progression free survival (PFS) in patients with Stable Disease (SD), or PR, at the time of first dosing of ES2B-C001 alone or in combination with the adjuvant according to RECIST 1.1. Disease-free survival (DFS) in patients with CR at the time of first dosing of ES2B-C001 alone or in combination with the adjuvant according to RECIST 1.1. Overall survival (OS) 			

4 Trial Design

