4.2 Rationale for Trial Design

This Phase 1 clinical trial is designed to determine safety, and tolerability of adjuvanted and non-adjuvanted ES2B-C001 to establish a maximum tolerated dose for this novel HER2-directed

Clinical Study: ES2B-C001-S01 EU CT No.: 2024-516333-12-00

vaccine in breast cancer patients. The primary rationale for conducting such phase 1 studies is to obtain sufficient information about safety and preliminary efficacy such as immunogenicity and antitumor activity to permit the design of subsequent well-controlled, scientifically valid phase 2 studies. The number of subjects included in such phase 1 trials is small, just enough to determine the safety, proper tolerated dose, and method of administration of the IMP, with or without adjuvant, for a next phase study. Enrollment in this FiH trial will be fully staggered in each of the populations. Repeated safety evaluations will be conducted during pre-dosing calls between PI(s), CRO medical monitor, and Sponsor, where safety and reactogenicity data from the first patient of each cohort will be reviewed. Additional safety evaluations will be performed at DSMB meetings to ensure a progression according to 3+3 design through a limited number of dose levels guided by safety. After accumulation of safety data across the dose levels, a maximum tolerated dose (MTD) will be established or if no unacceptable side effects or DLTs occur up to the highest dose level cohort, MTD will be determined as the maximum administered dose (MAD) level.

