4.3.1 Dose escalation rules

Dose escalation to a higher dose will be driven by an evaluation by the DSMB. At the time of DSMB evaluation, the last patient in the current dose level cohort must have received the 2nd dose and must have accumulated safety data for 8 weeks following the first dose. This allows for the DLT evaluation period to include an assessment of a potential delay in dose 2 due to toxicity concerns, as described for DLT number 5 in Section 4.3.2.

If one of the 3 patients in a dosing cohort experiences a DLT, 3 additional patients are added to the same dose level cohort. If 2 or more patients among these 6 patients experience DLTs, no further dose escalation can occur, and lower dose levels can be further explored. Dose escalation will continue until not more than 1 out of 6 patients experience DLT in a dose level cohort or the highest dose level group has completed treatment or no trial stopping criterion has been met. See Figure 2.

[figure not shown]

Figure 2: Dose-escalation according to a 3+3 design

Dose escalation will continue until not more than 1 out of 6 patients experiences a DLT in a dose level cohort (see DLT definitions in Section 4.3.2) or the dose level of

Clinical Study: ES2B-C001-S01 EU CT No.: 2024-516333-12-00

treatment has been completed (maximum administered dose MAD) or a trial stopping criterion has been met. The stopping criteria for dose escalation and trial are provided in Section 7.

Patients experiencing DLT will have their administration of adjuvanted or non-adjuvanted ES2B-C001 discontinued. These patients are allowed to remain in the trial to follow safety, disease progression and immune response. The DSMB will convene and recommend whether a re-start of these patients' treatment is advised and if a dose reduction may be required.

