7.5 Criteria for Temporarily Delaying Enrollment in the Trial and Stopping Rules

Enrollment of new patients in the trial will be temporarily halted if 2 or more out of 6 patients experience DLTs in the same dosing group (as per Section 4.3.2).

In these cases, DLT level has been reached and enrollment at that dose level cannot continue if DLTs are confirmed. The DSMB will review all available, accumulated safety data and recommend further course of action and potentially identify intermediate lower doses for further testing.

The trial includes following trial stopping criterion:

- DSMB recommendation based on patients' medical data and intolerable toxicities.
- Decision from the sponsor to terminate the trial.

8 Trial Assessments and Procedures

For timing of assessments and procedures, refer to the SoA presented in Table 1 (Section 1.3).

Clinical Study: ES2B-C001-S01 EU CT No.: 2024-516333-12-00

In the event of a significant trial-continuity issue (e.g., caused by a pandemic), alternate strategies for patient visits, assessments, medication distribution and monitoring may be implemented by the sponsor or the investigator, as per international, national or local health authority/ethics requirements.

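### Section 9.3.1 defines the MTD as the lowest dose with a DLT rate of at least 33%, which in a cohort of 6 is the dose at which Sections 4.3.1 and 7.5 stop

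*Protocol*

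**What the plan says.** The primary objective (Protocol Section 3, Table 3) is "To determine the safety, tolerability, maximum tolerated dose (MTD) for ES2B-C001 alone or in combination with the adjuvant". Section 9.3.1 fixes how that dose is found, separately for each patient population and on the Safety Set: it is the "lowest dose level at which ≥33% of patients have record of DLT".

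The decision rules stand elsewhere:

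- Section 4.3.1, expansion: "If one of the 3 patients in a dosing cohort experiences a DLT, 3 additional patients are added to the same dose level cohort".
- Section 4.3.1, stop: "If 2 or more patients among these 6 patients experience DLTs, no further dose escalation can occur". Lower dose levels can then be explored.
- Section 7.5, for 2 or more of 6 patients with a DLT in the same dosing group: enrollment is halted temporarily, and "DLT level has been reached and enrollment at that dose level cannot continue if DLTs are confirmed".
- Section 4.2, no toxicity: "if no unacceptable side effects or DLTs occur up to the highest dose level cohort, MTD will be determined as the maximum administered dose". The same section gives the purpose of such a trial as being to "determine the safety, proper tolerated dose, and method of administration of the IMP, with or without adjuvant, for a next phase study".

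**The concern.** A maximum tolerated dose is a dose that passed. Section 4.2 uses the term that way when it falls back on the maximum administered dose (MAD). Section 9.3.1 instead picks the lowest dose that failed.

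An SAP cannot repair this quietly, because the protocol itself fixes the definition. An SAP that follows it carries the error forward; one that departs from it contradicts the protocol on the primary objective. What is at stake is the dose carried into the next study: the reported MTD would be a level at which this protocol stops enrolling.

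**Working it through.** **Step 1. The threshold against the possible counts.** Cohort sizes are 3, 6 or 9 (Section 4.1). The observed rate is x/n, compared with 33%.

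| n | Highest count below 33% | Lowest count meeting 33% | Decision text at that lowest count |
|---|---|---|---|
| 3 | 0/3 = 0% | 1/3 = 33.3% | 4.3.1: add 3 patients |
| 6 | 1/6 = 16.7% | 2/6 = 33.3% | 4.3.1: no further escalation; 7.5: dose closed if DLTs are confirmed |
| 9 | 2/9 = 22.2% | 3/9 = 33.3% | no limit stated for 9 |

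At n = 6 the MTD condition and the stopping condition are the same event. This needs no assumption about true rates.

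**Step 2. How often a stopped dose would be named.** Table 14 may hold the sponsor's scenarios, but its body is not shown, so the true DLT rates below are assumptions. The model is a plain three-level 3+3: 0/3 go up; 1/3 expand; 1/6 go up; 2 or more of 3, or of 6, stop. Stopping at 2/3 or 3/3 is the usual convention; the visible text speaks only of 6 patients, and Figure 2 is not shown. Expansion to 9, backfilling, replacement, intermediate doses and early termination are not modelled.

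For a dose with true rate p, let b0 = (1−p)³ and b1 = 3p(1−p)². Then:

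- passes: b0 + b1·b0
- stopped at 6 patients: b1·(1−b0)
- stopped at 3 patients: 1 − b0 − b1

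Worked case, rates 5/15/30%:

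| Dose | p | Passes | Stopped at 6 | Stopped at 3 | P(dose reached) |
|---|---|---|---|---|---|
| 1 | 0.05 | 0.9734 | 0.0193 | 0.0073 | 1 |
| 2 | 0.15 | 0.8138 | 0.1255 | 0.0608 | 0.9734 |
| 3 | 0.30 | 0.4943 | 0.2897 | 0.2160 | 0.7922 |

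- Stopped at 6: 0.0193 + 0.9734×0.1255 + 0.7922×0.2897 = 0.371
- Stopped at 3: 0.0073 + 0.9734×0.0608 + 0.7922×0.2160 = 0.237
- No dose stopped: 0.7922×0.4943 = 0.392. Of this, no DLT at all is 0.8574×0.6141×0.3430 = 0.181, leaving 0.211 with at least one isolated DLT.

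The same steps for each set of assumed rates:

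| Assumed rates | Stopped dose named, at 6 | Adding 2/3 and 3/3 | No dose stopped, no DLT | No dose stopped, isolated DLT |
|---|---|---|---|---|
| 2/5/10% | 0.086 | 0.122 | 0.588 | 0.290 |
| 5/15/30% | 0.371 | 0.608 | 0.181 | 0.211 |
| 10/25/45% | 0.472 | 0.873 | 0.051 | 0.076 |

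**Step 3. Size of the error in dose.** Take the trials in which dose 2 or 3 is stopped at 6 patients. At 5/15/30% the weights are 0.9734×0.1255 = 0.1221 for dose 2 and 0.7922×0.2897 = 0.2295 for dose 3. The mean true DLT rate at the named dose is (0.1221×15% + 0.2295×30%)/0.3516 = 25%. One level below it is (0.1221×5% + 0.2295×15%)/0.3516 = 12%. The other two scenarios give 9% against 4% (2/5/10%) and 34% against 17% (10/25/45%).

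**Step 4. The paths with no stopped dose.** Where every level stays below 33%, Section 9.3.1 names no dose. Section 4.2 supplies the MAD, but on its wording only when there were no unacceptable side effects or DLTs. A trial with, say, 1/6 at one level and no stopped dose is covered by neither section. This is a gap, not a contradiction.

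**Step 5. A cohort left at 1/3.** It meets 33.3% although Section 4.3.1 only expands there. This matters only if the trial ends in mid-cohort, for example through "Decision from the sponsor to terminate the trial" (Section 7.5).

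**The case against.** The strongest reply is that Section 9.3.1 steers nothing. Dosing follows Sections 4.3.1 and 7.5 and the DSMB, and DLT counts by dose are reported regardless, so a careful reader can recover the right dose. No visible text makes the reported MTD the phase 2 dose automatically. All of that is true and limits the harm to the reported result. It does not make the definition correct, and the MTD is named in the primary objective.

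The halt in Section 7.5 is also temporary until the DLTs are confirmed, and the DSMB judges whether reported events meet the criteria (Section 10.7). That condition should be kept in mind, but confirmed DLTs close the dose and Section 9.3.1 still names it.

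On the figures, every true rate is assumed and the total swings from 12% to 87% over three scenarios, so they illustrate and do not estimate. Separating stops at 6 from stops at 3 is somewhat artificial, since 2 DLTs in the first 3 patients already guarantee at least 2 of 6; the total is the more coherent number. The gap for isolated DLTs is secondary, because Figure 2 and the DSMB charter may address it. The 1/3 case is an ordinary interim state unless the trial stops there. None of these points touches Step 1.

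**Conclusion.** The concern holds. In a cohort of 6, Section 9.3.1 names as MTD exactly the dose at which escalation is barred and, once DLTs are confirmed, enrollment ends. No visible part of the protocol corrects it, and Section 4.2 treats the MTD as a dose that was tolerated. This follows from the text and the arithmetic 1/6 < 33% ≤ 2/6 alone.

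How often it would bite depends on the unknown DLT rates and on a plain 3+3. When dose 2 or 3 is stopped at 6 patients, the named dose carries on average about twice the true DLT rate of the level below in the three scenarios. If the first level is the one stopped, there is no lower planned level to name. The definition should be corrected before any MTD is reported.

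**What to change.** In Section 9.3.1, define the MTD as the highest dose level studied that was not rejected under Sections 4.3.1 and 7.5 (at most 1 of 6 patients with a DLT) and that the DSMB did not judge to have unacceptable toxicity. Then state:

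- **Cohorts of 9:** the limit that applies, for example at most 2 of 9 (22.2%). This is the sponsor's choice.
- **No level rejected:** the MTD is the MAD, including when isolated DLTs occurred, keeping Section 4.2's condition on unacceptable side effects. Align Section 4.2.
- **First level rejected:** no MTD is declared among the planned levels.
- **Size at the MTD:** whether a level with only 3 patients may be declared the MTD, or 6 are wanted.
- **Denominator:** keep the Safety Set, or define a DLT-evaluable set in Section 9.2.

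In the same edit, correct the two sentences in Section 4.3.1 under which escalation goes on until at most 1 of 6 patients has a DLT; they reverse the 2-of-6 rule beside them.

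The cost is wording in Sections 9.3.1, 4.2 and 4.3.1 and in the SAP, plus Section 9.2 only if a new analysis set is chosen. The redefinition itself needs no extra patients or data. Requiring 6 patients at the MTD, if the sponsor wants that, could add up to 3.
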